### 3.3 Early Withdrawal of Subjects

#### 3.3.1 Criteria for removal from study

It is possible we will withdrawal participants from the study if they are unwilling to follow COVID-19-

related safety procedures during the mandate, become injured and cannot exercise or if they are asked by their Primary Care Provider to suspend exercise. The Principal Investigator reserves the right to remove a participant from the study for any reason, based on their discretion, particularly a belief that continued participation exposes them to unnecessary risk. Also, participants have the right to withdraw themselves at any time and halt all study-related activities permanently.

Other withdrawal criteria include: unwillingness to follow exercise protocol during sessions, unwillingness to complete the baseline assessment survey and/or return the accelerometer to study staff, withdrawal of consent by subject, development of a medical problem that would exclude them from the study (e.g., heart disease).

### **3.3.2 Follow-up for withdrawn subjects**

If the participant contacts us that they want to withdraw from the study, we will ask them to write a note and email it or put it in the mail documenting their desire to withdraw. Once we receive the letter, subjects will be withdrawn immediately. Subjects withdrawn will not have additional intervention or data collection activities schedule. They will not be replaced. For the focus groups, we will replace subjects who are withdrawn.

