As result of an unforeseen, COVID-19-related, prolonged exercise intervention cancellation (occurring between the dates of January 10, 2022 and February 21, 2022, following Penn State University mandates to pause all in-person human subjects research) and halt in the normal delivery of the exercise intervention sessions (occurring between the dates of February 21, 2022 and April 4, 2022, in an effort to recondition subjects to the exercise interventions and mitigate the risk of injuries), participants among the 2021 cohort may be requested to continue his or her study participation beyond the 12-month time point, to achieve six (6) continuous months of normal exercise intervention delivery between the months of February 2022 and August 2022. As result of the aforementioned effects of the COVID-19 pandemic, the study will treat this 6-month period as an individual 6-month study entity, completing the listed 9- and 12-month measurements (7.2 Study Procedures, RCT) with subjects at the 3- and 6-month post-resumption of the normal delivery of exercise intervention time points, respectively.

Participants among the 2019 cohort enrolled in the trial between the months of June and December 2019. Exercise intervention-related activities began in the month of September 2019 and continued through February 2020, prior to being halted as result of the onset of the COVID-19 pandemic. 6-month study visits occurred between the months of December 2020 and February 2020, prior to being halted as result of the onset of the COVID-19 pandemic. 12-month study visits did not occur among participants in the 2019 cohort, as result of the prolonged, COVID-19-related suspension of in-person human subjects research.

Participants among the 2021 cohort primarily enrolled in the trial between the months of June and October 2021. Exercise intervention-related activities began in the month of July 2021 (among subjects first to enroll in the study) and continued through December 2021, prior to being halted as result of the COVID-19 case count surge and subsequent College of Medicine (COM) mandate to pause all in-person human subjects research. The aforementioned in-person human subjects research pause rendered the 6-month study visits not feasible (due to COM mandates), disrupting data collection activities considerably. Following a 3-month halt in the normal delivery of the exercise intervention sessions between the dates of

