## 8.3 Statistical methods

The analysis of the main outcome measure will be performed by intent-to-treat, in which changes between baseline and twelve (12) full months of exercise intervention participation will be compared by conditions. Student's t-test will be used, though adjustment may be needed for any variables not controlled through randomization. If it is determined that the groups, by chance, are significantly different on other covariates, then we will include those covariates in secondary analyses.

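### Sections 3.3 and 8.3: staff removal is not separated from withdrawal of consent for data, and the intent-to-treat t-test has no missing-data method and no outcome time that fits every cohort

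*Combined protocol and SAP*

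**What the plan says.** Section 3.3.1 opens with discretionary removal: "It is possible we will withdrawal participants from the study", with reasons that include having "become injured and cannot exercise or if they are asked by their Primary Care Provider to suspend exercise". It then lists further withdrawal criteria, among them "unwillingness to follow exercise protocol during sessions" and a new excluding medical problem, in the same list as withdrawal of consent.

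Section 3.3.2 is the only rule on follow-up after withdrawal. It describes a written note from a participant who wants to leave, adds "Once we receive the letter, subjects will be withdrawn immediately", and continues: "Subjects withdrawn will not have additional intervention or data collection activities schedule". RCT participants who are withdrawn are not replaced.

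Section 8.3 says "The analysis of the main outcome measure will be performed by intent-to-treat". The comparison uses Student's t-test, and the section describes what is compared as follows: "changes between baseline and twelve (12) full months of exercise intervention participation will be compared by conditions". The only adjustment it mentions is for covariates. Neither 8.3 nor any other section describes imputation, a likelihood-based model or a sensitivity analysis for missing outcomes.

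On the visits that took place, 7.1 (RCT: COVID-19 Design Modifications) records that "12-month study visits did not occur among participants in the 2019 cohort", and that the 6-month visits of the 2021 cohort were not feasible. Section 7.2.17 moves the 2021 cohort's 12-month measures to 6 months after normal sessions resumed.

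**The concern.** An intent-to-treat comparison needs outcomes, or a stated way to handle their absence, for everyone randomised. Injury, advice to suspend exercise and refusal of the session format all arise after randomisation, and they can depend on whether the assigned activity is team sport or a class. If such people are removed and then not measured, those left in each arm may no longer be comparable.

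More than VO2max is at stake. MVPA shares Aim 1 with VO2max and can be collected by a mailed accelerometer. Injury is an Aim 2 outcome and is also compared by condition under 10.6. A rule that ends injury reporting when someone is removed for injury loses follow-up where it is most informative.

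A second, separate problem lies in 8.3. Its outcome time is expressed as months of participation rather than as a visit, and the pandemic interruptions mean this cannot be applied uniformly.

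**Working it through.** **Step 1: who is covered by 3.3.2.** Two readings are open.
- *General.* The section heading refers to withdrawn subjects without qualification, and 3.3.1 uses withdrawal for staff removal as well as for consent. Removed people then have no later data.
- *Narrow.* The sentence follows the written-note procedure, so it may mean only those who wrote in. Follow-up of removed people is then not stated anywhere.

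The two routes are not separated on either reading.

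**Step 2: what the t-test can use.** A t-test on change needs both a baseline and a 12-month value. With no method stated for a missing 12-month value, only people who have one can enter.

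**Step 3: the plan's own figures.** The RCT target of up to 470 in 8.1 cannot be reproduced, because no SD, alpha, power or loss rate is given for the RCT. The one loss figure, 8/50 = 16%, belongs to the feasibility studies. The removal rates below are therefore assumptions.

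**Step 4: size of a shift.** In one arm let p be the share removed, C the mean change in completers and R the mean change in removed people. The all-randomised mean is (1 - p)C + pR = C - p(C - R). With gap = C - R, arm 1 PlayFit and arm 2 Group Fitness:

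shift = completers' difference - all-randomised difference = p1 x gap1 - p2 x gap2.

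Section 8.2 expects at least 4 units in Group Fitness and at least 2.5 more in PlayFit, so 4 + 2.5 = 6.5. These are taken as completers' gains. If removed people gain nothing, the gaps are 6.5 and 4. If they gain half, the gaps are 3.25 and 2.

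| Removed, PlayFit v Group Fitness | Shift, no gain | Shift, half gain |
|---|---|---|
| 10% v 10% | 0.65 - 0.40 = 0.25 | 0.325 - 0.20 = 0.125 |
| 10% v 5% | 0.65 - 0.20 = 0.45 | 0.325 - 0.10 = 0.225 |
| 20% v 20% | 1.30 - 0.80 = 0.50 | 0.65 - 0.40 = 0.25 |
| 5% v 10% | 0.325 - 0.40 = -0.075 | 0.1625 - 0.20 = -0.0375 |

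In the no-gain column the first three rows are 10%, 18% and 20% of the planned 2.5. A completers' difference of 2.5 would correspond to 2.25, 2.05 and 2.00 among all randomised. Equal removal rates do not give zero, because the expected gains differ between arms. The last row shows that the sign can reverse.

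**Step 5: precision.** With up to 470/2 = 235 per arm, 10% v 5% is about 24 v 12 people. The standard error rises by the factor sqrt((1/0.90 + 1/0.95)/2) = 1.04, about 4%. Bias matters more here than lost precision.

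**Step 6: twelve full months against the calendar in 7.1.**
- 2019 cohort: 1 September 2019 to 29 February 2020 is about 5.9 months, with no 12-month visit.
- 2021, July starter: 1 July 2021 to 10 January 2022 (6.3) plus 4 April to 30 September 2022 (5.9) = 12.2 months.
- 2021, October starter: 2.3 to 3.3 plus 5.9 = 8.2 to 9.2 months. Adding the reconditioning weeks (21 February to 4 April 2022, 1.4 months) gives 9.6 to 10.6.

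Section 7.1 also mentions August 2022 as an end. The later date used here is the more favourable to the plan.

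**The case against.** The best defence is that 3.3.2 reads in sequence. Its sentence on data collection comes directly after the written note, and 3.3.1 says participants may leave and end all study activity for good. On that reading, stopping data collection simply respects withdrawn consent. This is plausible, and it stands to this extent: a reader might infer that the protocol orders staff-removed people to be dropped from follow-up, and the text does not establish that. What remains is that their follow-up is either ended or left unsaid.

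The exposed group may also be small. Removal is discretionary. People who stop attending are not removed but are contacted up to five times (7.2.13), and those who cannot attend a visit are still asked for accelerometry and surveys (7.2.16). Aim 2 expects similar injury rates. All of this stands, and it limits the size. It does not answer the point, because 7.2.16 serves people still in the study and its fallback yields no VO2max.

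Silence in 8.3 is not a specification of complete-case analysis, and a reader should not report it as one. The restriction to people with a 12-month value follows from the test named, unless a method is added.

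The outcome time in 8.3 could be taken as an adherence condition, or as fitting no cohort. The documents support neither. Section 7.2.11 speaks of extending participation to reach 12 months, so a shifted time point is a reasonable reading, and a July 2021 starter does reach about 12 months. The misfit is confined to 2019 and later 2021 starters. The missing 2019 visits come from the pandemic suspension, and rewriting 3.3.2 would not have prevented them.

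**Conclusion.** The point holds in a limited form and should be fixed. Sections 3.3.1 and 3.3.2 do not separate stopping the exercise programme from withdrawing consent for measurement. Section 8.3 pairs intent-to-treat with a test that cannot include people lacking a 12-month value, and states no method for them. Its outcome time suits only part of the 2021 cohort.

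The direction and size of any bias cannot be known from the documents. Under the assumptions that removed people gain nothing and completers gain 6.5 and 4 units, removal of 10% to 20% per arm, or 10% v 5%, shifts the difference by 0.25 to 0.50 units against the planned 2.5. Smaller gaps give smaller shifts, and the sign can reverse if Group Fitness loses more. A reader might infer that removal could by itself create or cancel the planned effect. None of these illustrations reaches 2.5, and no removal rate is given that would support the inference. Confidence is medium, mainly because the narrow reading of 3.3.2 is plausible.

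**What to change.** 1. In 3.3, distinguish participants who have stopped exercise sessions from those who have withdrawn consent for data collection. Leave the criteria for stopping exercise as they are.
2. Unless consent for data collection is withdrawn, continue scheduled accelerometry, REDCap surveys and monthly injury surveys through the remote procedures already in 7.2.14 and 7.2.16. Do in-person tests, including VO2max, only where existing procedures permit.
3. In 8.3, define the outcome by protocol visit for each cohort. For 2021 this is baseline and the 12-month measures taken 6 months after resumption. State that 2019 supplies no observed 12-month VO2max, and report its 6-month data separately. Neither cohort described in 7.1 had in-person visits held at both 6 and 12 months, so the data can hardly inform a link between the two.
4. Analyse by assigned arm with a baseline-adjusted model that handles missing outcomes, either likelihood-based or by multiple imputation. Add a missing-not-at-random sensitivity analysis for VO2max, varied separately by arm, with a range that covers no gain in each: from 0 to about -6.5 units for PlayFit and from 0 to about -4 for Group Fitness. Report withdrawals by arm, cohort and reason.

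The cost is protocol and consent wording, a short rewrite of 8.3, a few retained remote follow-ups and some extra analysis. The gain is mainly in MVPA, injury and survey outcomes. Little VO2max is recovered in people who cannot be tested, and visits already lost in the 2019 and 2021 cohorts cannot be restored.

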## 4.0 Recruitment Methods

### 4.1 Identification of subjects

We will send letters to patients of the Penn State Health, who reside in the zip codes of interest. Mailing lists will be generated by EIM. Patients age 18-50 who reside in a 10 mile radius around the exercise sites will be sent a letter. We, too, will generate mailing lists by EIM for recruitment of patients aged 51-70 years old. We will also place advertisements in newspapers, Facebook pages and communications from township park departments, schools or other community messaging print medium. We will also post printed advertisements (i.e., flyers) in public spaces frequented by potential participants. We will also use radio advertisements and advertisements when callers are on hold with the phone system phone system at Penn State Hershey. Of note, there is no specific maximum age, but participants to date in the pilot work have been under 50 years of age. If older participants hear about the study, they will be screened and treated the same as those who respond to a letter and are younger. For focus groups, participants in our prior research projects of PlayFit, who have previously given us permission to contact them for future studies, may also be called by phone to seek their participation.

We will also mail to potential subjects using a third-party list from a marketing company, such as Lorton Data, limited to those that live nearby the exercise site. When possible we will partner with community organizations that can send IRB-approved recruitment letters to members of their community, such as to parents of school students in the case of the Middletown Area Recreation Alliance.

### 4.2 Recruitment process

Interested participants will call our toll-free number and, if interested, be screened.

### 4.3 Recruitment materials

RCT:

Recruitment letter.

Feasibility Study:

Recruitment letter. We have created recruitment letters for each feasibility study (Adolescent, Depression, and Older Adult). These will be mailed to Penn State Health (PSH) patients identified by EIM who meet the age criteria (PSH patients aged 51-70 for the Older Adult Feasibility Study, PSH patients aged 10-12 for the Adolescent Feasibility Study, and PSH patients aged 18 or older meeting the inclusion criteria for the Depression Feasibility Study). More letters will need to be mailed for the Depression Feasibility study, as rates of depression among clinical populations are approximately 10% (6% for men, 12% for women). In the interest of maximizing recruitment success, we have created more than one version of recruitment materials for the Depression Feasibility study. Specifically, two different versions of the recruitment letter were developed; the first letter uses language focusing on “depression” and “mood” improvement while the other letter focuses more generally on “stress.” There is still some stigma related to labels for mental health disorders such as “depression,” which may limit the response rate of otherwise interested patients. However, it is also possible that patients experiencing depression may also be uniquely interested in the study due to the direct language surrounding depression/mood relief in the letter. Alternatively, “stress” is a more general term, that while related to depression, is universally experienced and carries less stigma. Overall, we do not know whether directly discussing depression versus stress diminishes or aids recruitment. We will send both letters simultaneously to maximize recruitment success in the shortest possible time and ultimately learn which messaging format is most effective via comparison of response rates; this will inform our future approaches to recruitment messaging. Recruitment letters for the Depression Feasibility study will include signature from [name]. Recruitment letters for the Adolescent Feasibility study will include signature from [name].

### 4.4 Eligibility/screening of subjects

## Focus groups

Interested subjects will be screened by phone by research staff who will read the phone screening document which will ensure eligibility and will inform them of study procedures. If eligible and interested in participating, they will be scheduled to attend one of the focus groups.

[figure not shown]
## RCT

Interested individuals who initiate contact with research staff via email—following receipt of a recruitment letter—will first be provided with an expectations/project summary document outlining next steps associated with the research. Those who initiate contact with research staff via phone call will be provided with the project summary document at the conclusion of the screening phone call, if deemed eligible. Individuals who remain interested in participating will be screened by phone by research staff who will read the phone screening document which will ensure eligibility and will inform them of study procedures. If eligible with continued interest in participating, they will be asked to sign consent electronically prior to the baseline visit, and then collect measurements at the baseline visit.

## COVID-19 Design Modifications

Interested subjects will be screened by phone by research staff who will read the COVID-19-specific phone screening content which will ensure eligibility and will inform them of COVID-19-specific study procedures. If the interested subject discloses a diagnosis of or positive test for COVID-19 within the previous 6 months of the phone screening, research staff will inform them of study procedures related to the Return to Play After COVID-19 screening algorithm (Figure 1). If the interested subjects indicates a negative response relating to diagnosis of or positive test for COVID-19, research staff will read the COVID-19 Supplemental Questionnaire which will ensure eligibility.

Figure 1. Return to Play after COVID-19 Algorithm

Algorithm based on current recommendations from: 1) PlayFit Study DSMB Members; 2) Study Physician, [name], MD; and 3) the ACC, AMSSM, and NFHS. These recommendations are subject to change as more evidence on COVID-19 myocarditis becomes available. Any subject who develops signs of clinical instability should be directed to the emergency department. If never symptomatic, the 14-day period begins at the time of a positive test. If there is return of any symptoms, the 14-day asymptomatic period restarts.

### Feasibility Study

Interested subjects will be screened by phone by research staff who will read the phone screening document which will ensure eligibility and will inform them of study procedures. If eligible and interested in participating, they will be asked to sign consent electronically prior to attending the initial in-person visit.

## 5.0 Consent Process and Documentation

### 5.1 Consent Process

#### 5.1.1 Obtaining Informed Consent

##### 5.1.1.1 Timing and Location of Consent

###### RCT + Older Adult, Major Depressive Feasibility Studies

Participants will individually review the consent form with one of the research coordinators via phone call. Research coordinator will individually review the consent form with participants as outlined per Penn State University's eConsent procedures and answer any questions; individuals will be requested to sign electronically. Research coordinator will provide a signed copy of the consent form via email at the conclusion of the phone call in order to allow participants to keep for their records. [name] will not participate in the consent process. For adolescent participants, a parent or guardian will need to be present throughout the full duration of the phone call to review and sign the consent form. In addition, the adolescent child will provide assent in the same form.

###### Adolescent Feasibility Study

Potential participants will individually review the consent form with one of the research coordinators via phone call. Of note, research coordinator will email a copy of the consent form to the individuals (parent/guardian for child and child) prior to the phone call to assist with the phone call review and provide the individuals with ample additional time to review the form prior to signing at the first in-person visit, should they wish. Research coordinator will individually review the consent form with potential participants and answer

any questions. Research coordinator will provide a consent form at the project site, and the individuals will be asked to sign. A copy of the consent form will be provided to participants to keep for their records. [name] will not participate in the consent process.

#### **5.1.1.2 Coercion or Undue Influence during Consent**

##### **RCT**

As outlined per Penn State University's eConsent procedures, participants will be emailed a copy of the consent form upon the start of the phone call review. They will be encouraged to ask questions during the consent process on a one on-one basis with the study staff. They can withdraw from the study at any time. [name] will not participate in the consent process.

### **5.1.2 Waiver or alteration of the informed consent requirement**

The study team is requesting a waiver of informed consent to allow for recruitment from clinic schedules and to access the subjects' medical charts.

## **5.2 Consent Documentation**

### **5.2.1 Written Documentation of Consent**

RCT + Older Adult, Major Depressive Feasibility Studies

Consent will take place via phone call as outlined per Penn State University's eConsent procedures. Research coordinator will individually review the consent form with participants, answer any questions, and obtain electronic written consent. A copy of the consent form will be provided to participants to keep for their records.

Adolescent Feasibility Study

Consent review will take place via phone call. Research coordinator will individually review the consent form with the individuals (parent/guardian for child and child) and answer any questions. Research coordinator will provide a consent form at the project site, and the individuals will be asked to sign. A copy of the consent form will be provided to participants to keep for their records.

Older Adult Feasibility Study

Research coordinator will individually review the consent form with participants, answer any questions, and obtain signed written consent. A copy of the consent form will be provided to participants to keep for their records.

